# **Background**

Currently, there are numerous orthopaedic graft adjuncts. These include bone morphogenetic proteins (BMP), autograft (iliac crest bone graft), graft substitutes, blood, bone marrow aspirate, platelet rich plasma (PRP), embryonic culture-expanded stem cells, and bone marrow aspirate concentrate (BMAC). Each graft adjunct involves unique advantages and disadvantages. Although BMPs and embryonic culture-expanded stem cells are osteoinductive and osteogenic, respectively, they are both associated with issues such as high cost and risk of side-effects. When using bone marrow aspirate, there is the issue of providing sufficient bioactivity via including a sufficient baseline concentration of stem cells. Hence, BMAC presents as a logical means of orthopedic grafting. Not only does BMAC demonstrate osteoinductive and osteogenic properties, but it also supplies a significantly higher stem cell concentration than sole BMA.

### History of Mesenchymal Stem Cells as Drivers of Tissue Regeneration

Mesenchymal stem cells (MSC) were initially thought to be the most important cell because early technology was only capable of expanding and differentiating an MSC *in vitro*. This led to the conclusion that MSCs were the drivers of tissue regeneration and if enough of them were expanded and transplanted, we would have clinical success regenerating tissue. However, FDA randomized clinical trials using cultured MSCs have failed and recent presentations have shown a negative dose effect in cardiac disease (i.e. high dose less effective than medium dose). The new understanding is that these cells can be best used for immune modulation rather than tissue regeneration. This is important to slow intervertebral disc degeneration.

### Current Understanding: Nonadherent Cells Drive Tissue Regeneration

It has been noted that nonadherent cells (bone marrow cells), not adherent cells (MSCs), drive tissue regeneration. For example, Chen et al. (1997) demonstrated that bone marrow cells (CD34+) can form fibroblasts, adipocytes, smooth muscle cells, and macrophages and can differentiate into functional osteoblasts. This finding was repeated by Mifune et al. (2008), in which they showed that CD34+ cells can differentiate to osteoblasts via an MSC intermediate.

Animal and clinical models have substantiated the finding that nonadherent cells (bone marrow cells) drive bone formation. Matsumoto et al. (2008) demonstrated that CD34+ cells delivered systemically or locally reliably formed functional bone greater than did controls. When these cells

PI: [name]

were delivered in a matrix, fewer cells were required than systemic administration. Further, Hernigou (2005) and Edgard and Einhorn (2011) recommended "the use of concentrated whole bone marrow, which includes other cells in the stromal and hematopoietic lineages...as they provide an optimized physiological and cellular milieu for the promotion of osteogenesis and angiogenesis."

Overall, non-adherent cells drive tissue regeneration by: (a) up-regulating cytokine release, which stimulates additional HSCs and MSCs from intact bone to the site of damage (Jung 2008); (b) releasing BMPs (Jung); (c) up-regulating production of VEGF and other cytokines that support angiogenesis and vasculogenesis (Mifune 2008); and, (d) directly forming bone by differentiating into MSCs and then osteoblasts (Matsumoto 2006, 2008).

### Advantages of Bone Marrow Aspirate Concentrate

In the bone marrow, there are two principal multipotent stem cells: stromal stem cells (SSC) and hematopoietic stem cells (HSC). There is roughly one SSC in every 250,000 cells in the marrow at age 35 and this ratio decreases with age. There is roughly one HSC in every 10,000-15,000 cells in the marrow (this ratio does not decrease with age). The issue is that with such a small concentration of SSCs and HSCs, without concentrating the BMA, there will be unpredictable healing, particularly in healing-impaired patients.

Hence, the use of BMAC is recommended. When provided in a clinical model, BMAC is given with allograft and this combination demonstrates the same angiogenic, osteoinductive, osteoconductive, and osteogenic properties as BMP. Further, BMAC exactly mimics and supplements the body's natural response to trauma by stimulating vasculogenesis and tissue regeneration.

## Conclusions of previous clinical models

BMP has been used since 2002 in the lumbar spine to promote bony fusion since its approval by the FDA for use in anterior lumbar interbody fusion, and is now approved for use in posterior and transforaminal approaches. BMP augment bony growth is promoting MSC and osteoprogenitor cell differentiation into osteoblasts, which is very similar to BMAC. In a 2015 systematic review of lumbar fusion rates with the use of rhBMP-2, Galimberti et al showed interbody lumbar fusion rates ranging from 97.8-93.6%. However, as detailed in a review of randomized clinic trials by Chrastil et al in 2013, despite high fusion rates, there may complications associated with BMP such as heterotopic ossification, radiculitis, and endplate osteolysis. While usage of BMP is attractive for avoiding autologous grafting—decreasing operative times, blood loss, avoiding donor site morbidity, and allowing for biologics in older, more morbid patients that may have a limited autograft supply.

Previous reports by Connolly et al., Gangji et al., Hernigou et al., and Gessmann et al. have also shown that high concentrations of adult stem cells from iliac crest bone marrow can enhance the rate and amount of bone formation. The authors report that technology that quickly and easily concentrates bone marrow stem cells 3 to 6 times harvested baseline concentrations makes practical the use of adult bone marrow stem cells in a spinal fusion. In a study by Gan et al., they found a 95% successful spinal fusion rate when 252 mL BMA harvested from the iliac crest was

PI: [name]

concentrated peri-operatively down to 45 mL enriched suspension. In contrast, the historical autograft fusion success rate ranges between 65-95%.

These studies conclude that both BMP and BMAC mimic and supplement the body's natural response to trauma by stimulating vasculogenesis and tissue regeneration. BMAC contains many cell types, while BMP contains only one, the question of superiority between the two methods of bone healing/remodeling stimulation is unanswered. As BMAC is autologous, there are no immuno-rejection side-effects or concerns regarding disease transmission.

### Preliminary Data

In an earlier study with unpublished results, 14 BMAC+allograft patients were compared to 3 ICBG. This randomized series determined radiographic fusion in 92.9% of cases among the BMAC+allograft and ICBG cohorts, suggesting no difference in fusion efficacy among these grafts. This study did not identify any difference between lumbar spinal fusion patients receiving ICBG versus BMAC+allograft during surgery, on the basis of patient-reported outcomes up to 1-year follow-up and fusion grading. Only higher SF-12 MCS scores at baseline among ICBG patients were sustained at 6-weeks and 6-months post-operative. These preliminary results are important given the controversy surrounding effective use of interbody grafts, but are not decisive especially when, for many surgeons, the choice is between BMP and BMAC.

# Our hypothesis is that:

For patients who undergo lumbar spinal fusion surgery with interbody support, the outcomes in terms of pre-operative measures, intra-operative measures, and post-operative measures in the investigational group (BMAC + allograft) will be similar to the compared BMP group and control group at 24 months postoperatively.

# **Study Objective**

To compare the efficacy of BMAC+allograft versus BMP versus autograft (control), we plan to pursue a prospective, blinded controlled study in which: BMAC+allograft or BMP or autograft will be randomized 1:1:1 ratio, respectively to certain patients undergoing a lumbar fusion by interbody support.

# **Study Design**

This study will be a prospective, randomized clinical study at a single-center, NYU Langone Medical Center. It is intended to compare and evaluate the efficacy of subjects who are either treated with (1) bone marrow aspirate concentrate (BMAC) and allograft or (2) recombinant human bone morphogenetic protein-2 (BMP) or (3) autograft (control) during lumbar spinal fusion with interbody support. The clinical, radiographic, and Health Related Quality of Life (HRQOL) outcomes will be assessed in operatively treated adult spinal degenerative disease patients undergoing lumbar spinal fusion.

### **Sample Size Analysis**

### PI: [name]

A power analysis was performed for sample size estimation, based on data from Bishop et al (N=132), comparing arthrodesis rate in autograft vs. allograft fusion groups[31]. In an effort to identify the number of patients needed in the current research project, a power analysis has been investigated with G\*Power 3.1.9.2:

### • Arthodesis rate one year post-operation (paired t-test):

The effect size (ES) in this study was 0.4, considered to be low using Cohen's (1988) criteria. With an alpha = .05 and power = 0.80, the projected sample size needed with this effect size is approximately N = 23.

Thus, our proposed sample size of N=60 (with 20 patients per arm; effectively 40 for t-tests between groups) will be more than adequate for the main objective of this study and should also allow for expected attrition

Completion rate of enrolled patients in our protocol is estimated to be 85% based on standard clinical follow up rates for lumbar Spinal Fusion patients at the investigators practices. Therefore, by enrolling 20, we expect at least 17 in each group.

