# **Costs to the Subject**

All of the tests (i.e. physical evaluation and imaging components) will be performed as part of the standard of care. The patient may want to discuss this with his insurance carrier in advance. The patient will be responsible for any co-payments and/or deductibles for services rendered.

The patient or his/her insurance company will be responsible for paying for the 1-year follow-up CT scan because it is part of standard care. Patients will have the option to refuse CT scan in which case they will be excluded from the primary data analysis but will be part of the secondary analysis.

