# **Data Analysis**

### Sample Size Justification

There are no previous studies with exact means in ODI for a BMAC group not the association between clinical outcomes and concentration of MSCs and CFUs. Therefore, assumptions had to be made. If the standard deviation for each group was assumed to be 10 and equivalence as within 12.8 (MCID), given 90% power and alpha=0.05, we would need 14 patients per group. However, if we assume equivalence as within 6 points, we would need 59 patients per group. We understand that assumptions greatly affect sample size, and therefore, our desired sample size of 60 patients is appropriate.

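### The fusion sample size of 23 does not follow from its stated inputs, which need 52 pairs (41 one-sided), and a paired test does not fit three independent arms

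*Combined protocol and SAP*

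**What the plan says.** The Sample Size Analysis takes an effect size of 0.4 from an external comparison of autograft and allograft (N = 132), without giving the fusion rates behind it. Under a sub-heading that names the one-year arthrodesis rate and a paired t-test, it concludes: "With an alpha = .05 and power = 0.80, the projected sample size needed with this effect size is approximately N = 23". Sidedness and the type of effect size are not stated. It goes on to say that N = 60 "with 20 patients per arm; effectively 40 for t-tests between groups) will be more than adequate for the main objective of this study". Completion is put at 85%: "Therefore, by enrolling 20, we expect at least 17 in each group".

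The Study Objective describes separate arms: "BMAC+allograft or BMP or autograft will be randomized 1:1:1 ratio, respectively to certain patients". Randomization Process and Research Design & Methods repeat the 1:1:1 allocation and mention no matching. Aim 1 makes CT fusion status at one year the primary outcome. The only between-group method given there is Student t-tests on changes from the pre-operative visit, and nothing is specified for fusion itself.

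A second calculation, in Sample Size Justification under Data Analysis, concerns equivalence on ODI. With an SD of 10 and a margin of 12.8 points, "given 90% power and alpha=0.05, we would need 14 patients per group". With a 6-point margin it gives 59 per group. It then calls a total of 60 appropriate.

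**The concern.** This is the only quantitative support that the protocol offers for its primary endpoint. Three things looked wrong.

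- At an effect size of 0.4, a paired t-test needs far more than 23 pairs.
- The outcome is a fused/not fused status compared between independently randomised patients, so no pairs exist.
- Forty patients split over two arms are not 40 pairs, so the remark about 40 patients for between-group tests does not repair the calculation.

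The direction of the hypothesis raises the stakes. Outcomes with BMAC plus allograft "will be similar to the compared BMP group and control group at 24 months postoperatively". That statement covers all outcomes at 24 months, and nowhere does the plan say that a non-significant fusion result will be taken as similarity. Even so, a small trial described as amply sized, with similarity as the expected finding, leaves that reading open, and the design could not support it.

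**Working it through.** **Inputs.** From the Sample Size Analysis: paired t-test, effect size 0.4, alpha 0.05, power 0.80, stated N = 23, 20 per arm enrolled and 17 expected. Both one- and two-sided tests were tried.

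**1. The plan's figure.** The required n is the smallest at which a t statistic with n − 1 degrees of freedom and noncentrality 0.4√n exceeds its critical value with probability 0.80.

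| | Two-sided | One-sided |
|---|---|---|
| Solution | 51.01, so 52 pairs | 40.03, so 41 pairs |
| Normal check, ((z for alpha + z for power)/0.4)² | ((1.960 + 0.842)/0.4)² = 49.1, so 50 | ((1.645 + 0.842)/0.4)² = 38.6, so 39 |
| Power with 23 pairs | 45% | 58% |
| Effect size giving 80% power with 23 pairs | 0.61 | 0.54 |

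Sidedness does not explain the gap. Values near 23 appear only if the test is changed or an input is added. Regression with one predictor and f² = 0.4 gives 22. A three-measure repeated-measures F test with f = 0.4 and zero correlation gives 22. A d of 0.4 with a within-pair correlation of about 0.785 gives 23.1, so 24 pairs. One-way ANOVA with f = 0.4 and three groups gives 63.3/3 = 21.1, so 22 per group. The plan states none of these, and the ANOVA reading would need more than the 20 per arm enrolled.

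**2. Independent arms.** Here 0.4 is read as a standardised difference between two arms (an assumption), with noncentrality 0.4√(n/2).

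| | Two-sided | One-sided |
|---|---|---|
| Needed per arm for 80% power | 99.08, so 100 | 77.97, so 78 |
| Power, 20 per arm | 23% | 34% |
| Power, 17 per arm | 20% | 31% |

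**3. Precision for a difference in fusion rates.** The plan gives no planning rates. For illustration, 94% and 85% come from Criteria for Action, where they are literature benchmarks. The low case of 65% comes from the background: "the historical autograft fusion success rate ranges between 65-95" per cent. The half-width is half the length of the Newcombe 95% interval, averaged over all possible outcomes by exact binomial enumeration.

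| Fusion rates in the two arms | 20 per arm | 17 per arm |
|---|---|---|
| 94% and 94% | 19.3 points | 21.4 points |
| 94% and 85% | 21.1 | 23.2 |
| 85% and 85% | 22.8 | 24.8 |
| 94% and 65% | 23.4 | 25.4 |
| 85% and 65% | 25.0 | 26.9 |

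**4. Power for a difference in fusion rates.** Two-sided Fisher's exact test, by enumeration:

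- 94% versus 85%: 5.8% with 20 per arm, 3.8% with 17.
- 94% versus 65%: 54% and 43%.

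For 80% power at 94% versus 85%, the pooled normal approximation gives [1.960√(2 × 0.895 × 0.105) + 0.842√(0.94 × 0.06 + 0.85 × 0.15)]²/0.09² = 180.9, so 181 per arm. Fisher's test has 76% power at 181 and needs 197.

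**5. The ODI calculation.** Two one-sided t-tests at 0.05, SD 10, true difference zero. At a margin of 12.8, 14 per group give 90% power, which reproduces the plan, and 20 give 98%. At a margin of 6, 20 per group give 18% power, and the plan's 59 give 89%. Twenty per arm therefore meets the wider margin only, and neither result bears on fusion.

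**6. Numbers analysed.** Under Costs to the Subject: "Patients will have the option to refuse CT scan in which case they will be excluded from the primary data analysis". The plan does not say whether its 85% completion already counts these patients, so fewer than 17 per arm may be analysed for fusion.

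**The case against.** The arithmetic itself is hard to contest. The best case on the other side concerns scope and presentation.

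- **Another basis for N = 60.** The recruitment section ties the 60 subjects to the investigator's caseload. This is true, and it is a reason to leave N alone. A caseload basis is about feasibility, however, and does not support a claim of adequacy for the primary endpoint.
- **Hypothetical harm.** No section commits to reading non-significance as similarity. That is correct. The demonstrated defect is the wrong number and the adequacy claim; the sentence on interpretation is a low-cost safeguard.
- **Choice of rates.** The 85% benchmark is for bone marrow aspirate, not concentrate. The background gives 95% for concentrated marrow and 93.6–97.8% for BMP, and the preliminary series 92.9%. This stands as a caution, but the effect is small: at 95% in both arms the half-width is 18.8 points with 20 per arm and 21.0 with 17. Quoting power only for 94% versus 85% would also be one-sided, so 94% versus 65% is shown too. Neither reaches 80%.
- **Other cures.** Recalculating for two independent proportions, or declaring the fusion comparison exploratory, would also remove the defect. That is so. The first needs a target difference that the plan does not give.
- **The ODI section is separate.** It openly admits that its assumptions drive the answer. Its rewording matters less than the correction to the fusion calculation.

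**Conclusion.** The concern holds. The stated inputs require 52 pairs two-sided or 41 one-sided, about twice the 23 given, and this needs no assumption beyond what the plan states. A paired test also has no place in a comparison of three separately randomised arms. The 20–34% power figures for independent arms assume that 0.4 is a between-group standardised difference. The half-widths of 19–27 points assume fusion rates of 65–94%, which are illustrative and not planning values. The right N for fusion cannot be derived from the documents, because no target difference is given. In none of the scenarios examined does the fusion comparison reach 80% power with 20 or 17 per arm, so the claim that 60 patients are ample for the main objective should be withdrawn.

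**What to change.** Keep N = 60 and change the wording in three places.

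**Sample Size Analysis.** Delete the paired t-test calculation and the adequacy claim, and do not carry the 0.4 forward. State instead:

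> The one-year CT fusion comparison is estimation of differences between independent proportions. Assuming, for illustration, fusion rates of 85–94% (the benchmarks in the stopping criteria), the expected half-width of the Newcombe 95% interval for a between-arm difference (half its total length) is about 19–23 points with 20 per arm and 21–25 with 17. It is wider if patients refuse CT or if autograft rates are lower (about 23–25 and 25–27 points at 65%). Fisher's exact test has about 4–6% power for 94% versus 85%, and 43–54% for 94% versus 65%. A non-significant difference will not be read as evidence of similarity.

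State here whether the 85% completion figure already counts CT refusals. The caseload basis for N = 60 can be cited as the feasibility reason.

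**Sample Size Justification.** Replace the closing statement with:

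> This calculation concerns ODI and not fusion. Twenty per arm meets the 12.8-point figure (14 per group) but not the 6-point figure (59 per group).

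If the 59 is kept, note that two one-sided t-tests give it 89% power, just under the stated 90%.

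**Aim 1.** Name the same interval as the method for fusion.

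No patients, visits or procedures are added. The cost is that fusion can no longer be presented as adequately powered, and the ODI claim holds only at the wider margin.

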### Age and Gender of Subjects

This prospective study will include both male and female patients over the age of 18 years old.

### **Racial and Ethnic Origin**

For the enrollment of this study, there are no racial or ethnic restrictions.

# **Vulnerable Subjects:**

There will be no vulnerable subjects in study.

### **Estimated Duration of Study**

3 years (1 year for subject enrollment; 2 additional years to complete 2-year follow-up)

### **Human Subject (Inclusion/Exclusion Criteria)**

#### **Inclusion criteria:**

- 1. Must be 18 years old or older
- 2. Scheduled for elective posterior or anterior and posterior spinal fusion of the lumbar spine with or without anterior interbody support
- 3. Failed at least 6 weeks of conservative care
- 4. ODI v2.1 score > 30%
- 5. No contraindication to BMAC (as per manufacturer)
- 6. Signed consent form

### **Exclusion criteria:**

- 1. Prior lumbar fusion surgery at operative level (prior discectomy and/or laminectomy allowed) at any time period, or prior spine surgery at any level 6 months before index recruitment surgery
- 2. Spondylolisthesis grade 3 or more

PI: [name]

3. Excluded patients with myelopathy, history of myelopathy, significant neurological compression, or neurological impairment in the cervical or thoracic spine

- 4. Incompetent or missing anterior arch at the affected level (e.g. laminectomy, pars defect)
- 5. Currently requires laminectomy at level of surgery
- 6. Facet joints at implant level are absent or fractured
- 7. Post-traumatic vertebral body compromise or acute fracture at implant level
- 8. Body mass Index (BMI) > 40
- 9. Known allergy to titanium
- 10. Paget's disease, osteomalacia, or any other metabolic bone disease
- 11. Use of medications or any drug known to potentially interfere with bone/soft tissue healing (e.g. chronic systemic steroids)
- 12. Unlikely to comply with the follow-up evaluation schedule
- 13. Subject has recent history (less than 3 years) of chemical substance dependency or significant psychosocial disturbance that may impact the outcome or study participation
- 14. Participation in a clinical trial of another investigational drug or device within the past 30 days
- 15. Systemic infection such as AIDS, HIV, and active hepatitis
- 16. Active malignancy defined as history of invasive malignancy, except if the subject has received treatment and displayed no clinical signs and symptoms for at least five years
- 17. Pregnant or planning to become pregnant during the length of study participation
- 18. Involvement in active litigation related to back problems at the time of screening (this does not apply to litigation required by no fault states)
- 19. Direct involvement in the execution of this protocol
- 20. Patients who have planned spinal surgery intervention after enrollment into study and throughout course of follow up

### Intra-operative exclusion

1. Any change in the surgical procedure PRIOR to surgery that violates the inclusion/exclusion criteria.

### Randomization Process

The process of randomization will be computerized and completed by an individual not associated with the study. The randomization will be performed at 1:1:1 ratio between the three arms. Sequenced and sealed envelopes or a similar randomization technology approach will be used. Given posterior, anterior and anterior-posterior surgical techniques will be randomly included in the three study arms, we anticipate equal stratification. However, if study arms show predominance to one surgical approach, attempt will be made to increase enrollment of patients of the unbalanced surgical approach.

